2.5.3 Handling of intercurrent events

Handling of intercurrent events of the primary efficacy and safety estimands is described in Section 1.2.1.

2.5.4 Handling of missing values not related to intercurrent event

Primary efficacy analysis in adults (safety run-in and expansion parts)

For a participant who completed at least 6 cycles of treatment or who discontinued treatment earlier before completion of 6 cycles (for reasons other than death, relapse or start of new antineoplastic therapy) and the response assessment on Cycle 7 Day 1 (after completing 6 cycles) or 6 months after start of study treatment (if 6 cycles were not completed) is missing or the response is "unknown":

- If no relapse (maintenance of CR or CRi) is documented at the subsequent response assessment (any time after Cycle 7 Day 1 or 6 months after study entry if 6 cycles are not completed), the participant will be considered a responder.
- If a relapse (no maintenance of CR or CRi) is documented in the subsequent response assessment (any time after Cycle 7 Day 1 or 6 months after study entry if 6 cycles are not completed), the participant will be considered a non-responder.
- If the subsequent response assessment (any time after Cycle 7 Day 1 or 6 months after study entry if 6 cycles are not completed) is also missing or the response is "unknown", the participant will be considered as a non- responder.

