6.2.2 Prohibited medication

During the course of study treatment, participants must not receive additional investigational drugs or devices, chemotherapy, DLI, other cellular therapies or any other therapies that may be active against cancer or modulate the immune response. Post treatment efficacy follow-up period will end, once a participant develops a hematologic relapse, or start of new therapy for AML.

Additionally, the use of systemic corticosteroids and/or immunosuppressive medications is not allowed while on study treatment unless given for the management of infusion-related reaction, treatment-emergent immune-related adverse events (irAEs), aGvHD and/or cGvHD.

Systemic corticosteroids required for control of infusion-related reactions or irAEs must be tapered and be at non-immunosuppressive doses (≤ 10 mg/day of prednisone or equivalent corticosteroid dose) before the next study administration. If more than 10 mg/day prednisone is used, sabatolimab should be interrupted until the participant receives 10 mg/day or less of prednisone. Topical, inhaled, non-absorbable, nasal and ophthalmic steroids are allowed.

For aGvHD and/or cGvHD, refer to Table 6-4.

The use of systemic steroids and/or other immunosuppressive drugs may be administered for prophylaxis against imaging contrast dye allergy (providing this is ≤ 10 mg/day prednisone or equivalent corticosteroid dose), or replacement-dose steroids in the setting of adrenal insufficiency, or for the management of transient exacerbation of other underlying diseases such as chronic obstructive pulmonary disease requiring treatment for ≤ 3 weeks.

The use of live vaccines is not allowed through the duration of the study treatment and 150 days after the last dose of sabatolimab. Inactivated vaccines, subunit, recombinant, polysaccharide and conjugate vaccines and toxoid vaccines are allowed.

In addition, prohibited medication related to azacitidine will apply according to local/global label.

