Note: If a treatment cycle is delayed at any time during the study, all study visits and safety and efficacy assessments should continue according to the appropriate number of calendar days measured from Day 1 of the previous cycle, or more often if clinically indicated. In the combination cohort, when treatment is resumed, the first day of azacitidine administration will be considered as D1 of the new treatment cycle and visit schedule will be shifted accordingly. If sabatolimab administration on Day 5 is delayed within a cycle due to toxicities, visit assessments for Day 5 should be shifted accordingly.

On PK collection days the windows and time points are provided in Section 8.5.2.

Participants who discontinue the study treatment for any reason should be scheduled for an end of treatment (EOT) visit within 14 days from the decision to permanently discontinue study treatment, at which time all of the assessments listed for the EOT visit will be performed.

For post-treatment follow-up information, please refer to Section 9.1.1.2.

Table 8-1 Assessment Schedule, Sabatolimab monotherapy cohort

Period	Pre- Screening	Screening		Treatment								Safety Follow-up	Post-Treatment Follow-up	
Cycle				cle 1	-	ele 2	Cycle 3	Cycle 4	Cycle 5	Cycle 6	Cycle 7 (and subsequent cycles up to Cycle 24)			
Days	NA	-28 to -1	D1	D15	D1 ±3	D15	D1 ±3	D1 ±3	D1 ±3	D1 ±3	D1 ±3	EOT	30,90,150 days	Every 12 weeks
Pre-screening Informed Consent	Х													
Informed consent		Х												
IRT Registration	Х	Х	Χ									Х		
Demography		Х												
Inclusion / Exclusion criteria		Х												
AML Disease History [aHSCT and GvHD (acute and chronic) history]		х												
MRD History ²		Х												
Other relevant Medical History /Current medical conditions		х												
Prior medications (including prior antineoplastic therapies, prophylactic DLI), surgery, and medical procedures		х							(continu	ous		X	

Period	Pre- Screening	Screening		Treatment								ЕОТ	Safety Follow-up	Post-Treatment Follow-up
Cycle				le 1	Cycle 2		Cycle 3	Cycle 4	Cycle 5	Cycle 6	Cycle 7 (and subsequent cycles up to Cycle 24)			
Days	NA	-28 to -1	D1	D15	D1 ±3	D15	D1 ±3	D1 ±3	D1 ±3	D1 ±3	D1 ±3	EOT	30,90,150 days	Every 12 weeks
Physical Examination		S	s	S	S	S	S	S	S	S	S	S		
Vital Signs		Х	Х	Х	Х	Х	Х	Х	Х	Х	X	Х		
Body Height		Х												
Body Weight		Х	Х		Х		Х	Х	Х	Х	X	Х		
Performance Status Score ³		Х	Х		Х		Х	Х	х	х	X	Х		

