Extramedullary disease assessment is performed via physical examination. Additional evaluation for extramedullary disease [eg, imaging, procedures (tissue biopsy, lumbar puncture), etc.] will be performed as clinically indicated per the investigator's assessment. Cerebrospinal fluid assessment and relevant imaging techniques may be performed, as clinically appropriate at the investigator's discretion, in case of symptoms suggestive of meningeosis leukemia, and/or prior history of central nervous system involvement with AML. In case of extramedullary disease (re-) appearance during the study, the lesions should be considered for confirmation by imaging or biopsy if technically and/or clinically feasible.

Assessment for the presence or absence of extramedullary disease will be performed at screening, and pre-dose on C2D1, C3D1, C4D1 and C7D1 and every 3 cycles D1 until Cycle 13 D1 and then every 6 months and as clinically indicated until relapse, start of a new anti-neoplastic treatment, death, lost to follow-up or withdrawal of consent. The presence or absence and physical location of extramedullary disease are to be recorded on the CRFs.

Participants can be assessed for disease response (bone marrow assessment, hematology, extramedullary disease assessment) at any time if clinically indicated, for example in case of suspicion of relapse. Therefore, more frequent efficacy assessments may be performed at the investigator's discretion, if medically indicated, and recorded as an unscheduled visit in the eCRFs. Clinical suspicion of relapse at any time will require an evaluation promptly, rather than waiting for the next scheduled assessment. In case of an unscheduled or delayed disease evaluation of any reason, subsequent assessments should be performed according to the originally planned schedule.

More frequent efficacy assessments, performed at the Investigator's discretion, should be recorded on the Unscheduled Visit CRFs. All assessments will be analyzed.

Table 8-3 Response classification in AML at a given evaluation time (based on IWG Cheson et al 2003, ELN 2017 Döhner et al 2017)

Response Category	Definition ¹		
Complete Remission	Bone marrow: blasts < 5%		
	Peripheral blood: No circulating blasts or blasts with Auer rods		
	No evidence of extramedullary disease (such as CNS or soft tissue involvement)		
	Neutrophils ≥ 1.0x10 ⁹ /L		
	Platelets ≥ 100x10 ⁹ /L		
Complete remission with	Bone marrow: blasts < 5%		

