12.4.4 Handling of missing values not related to intercurrent event

For the determination of the absence of evidence of hematologic relapse (ie, no evidence of bone marrow blasts ≥5%; no evidence of reappearance of blasts in the blood; no evidence of development of extramedullary disease) after 6 cycles of treatment, only the response assessment performed at Cycle 7 Day 1 or the response assessment performed 6 months after starting the study treatment is considered.

An adequate response assessment is considered any disease assessment indicating response status apart from "unknown" or "not done". Evaluation of response relies on bone marrow, peripheral blood, and extramedullary disease assessment. In case of missing data for the full assessment required to qualify for a given response or in case of a more than 7 days difference between bone marrow aspirate/biopsy assessments and hematology assessments of the same visit, the overall assessment "unknown" was assigned unless relapse was seen in at least one compartment (i.e. bone marrow or blood).

A participant will be considered with no evidence of hematologic relapse if an adequate response assessment indicates a complete remission (CR) or a complete remission with incomplete hematologic recovery (CRi) response; and even if one or several inadequate response assessments ("unknown" or "not done") have been documented prior to the current adequate response assessment.

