1.2.1 Primary estimands

For adults participants included in this study, there are two primary clinical questions:

- Safety: Does sabatolimab, administered as monotherapy at 400 mg and 800 mg Q4W dose levels, lead to an unacceptable level of toxicity [dose-limiting toxicity (DLT)], when given to treat participants with acute myeloid leukemia (AML) who have received an allogeneic hematopoietic stem cell transplantation (aHSCT), and are in complete remission but are MRD+ (per local assessment)?
- Efficacy: What is the effect of sabatolimab at the RDE, as monotherapy and in combination with azacitidine, on prevention of hematologic relapse (i.e., no evidence of bone marrow blasts ≥ 5%, no evidence of reappearance of blasts in the blood, no evidence of development of extramedullary disease) [i.e., maintenance of complete remission (CR) or CR with incomplete hematologic recovery (CRi)] in participants with AML at high risk of relapse (MRD positivity as per local assessment) after aHSCT regardless of treatment interruption or discontinuation during study and until use of donor lymphocyte transfusions (DLIs) or other new antineoplastic therapies?

For adolescent participants included in this study, there is one primary clinical question:

• Safety: Does sabatolimab administered as monotherapy at the recommended dose level for adults, lead to an unacceptable level of toxicity (DLT), when given to treat adolescents with AML who have received an aHSCT, have been tapered off of systemic immunosuppressive therapy at enrollment, and are in complete remission but are MRD+ (per local assessment)?

Justification: In this proof-of-concept study, the primary purpose is to determine whether or not the risk of developing GvHD, immune-related toxicities and other unacceptable toxicities is not exacerbated when sabatolimab is administered in the post-transplant setting. The activity of sabatolimab is assessed based on the absence of hematologic relapse (no evidence of any of the following: bone marrow blasts \geq 5%; reappearance of blasts in the blood; or development of

Novartis	Confidential	Page 13 of 35
SAP – Amendment 1		CMBG453F12201

extramedullary disease), which is the most clinically meaningful endpoint in this post-transplant setting where complete hematologic recovery may be delayed early post-transplant.

The **primary safety estimand for adult participants** included in this study is described by the following attributes:

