- 3. Treatment of interest: Treatment with sabatolimab or sabatolimab in combination with azacitidine taken for the entire study duration post aHSCT. One estimand for each of the two treatments of interest (sabatolimab in monotherapy and sabatolimab in combination with azacitidine) will be considered.
- 4. Handling of intercurrent events:

- Failure to complete 6 cycles of treatment due to death for any reason or relapse: a participant who dies or has a relapse before completing 6 cycles of treatment will be considered as a non-responder (composite variable strategy).
- Start of donor lymphocyte infusions (DLI) or a new anti-neoplastic therapy before completing 6 cycles of study treatment: a participant who starts a DLI or a new antineoplastic therapy before completing 6 cycles of treatment will be considered as a non-responder (composite variable strategy).
- Failure to complete 6 cycles of treatment due to reasons other than relapse and death for any reason (including due to adverse events, graft vs. host disease for example): all participants with an adequate response assessment (other than "unknown" response) will be taken into account regardless of any study treatment interruption or permanent discontinuation; for a participant who stops the study due to reasons other than relapse or death, we will ask the participant to perform a response assessment 6 months after starting study treatment; a participant with no evidence of hematologic relapse 6 months after starting treatment will be considered a responder (treatment policy strategy).
- 5. Summary measure for the primary efficacy estimand is the proportion of participants with no evidence of hematologic relapse with its exact 95% confidence interval for each of the two study treatment of interest: sabatolimab in monotherapy and sabatolimab in combination with azacitidine. The trial will be successful if at least one of the treatments of interest (sabatolimab monotherapy or sabatolimab in combination with azacitidine) meets both statistical and clinical significance.

The **primary safety estimand for adolescent participants** included in this study is described by the following attributes:

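### SAP 2.5.4 fills a missing primary response assessment from a later one without a cut-off at DLI or new antineoplastic therapy, and SAP Section 4 does not record the change from the protocol (minor)

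*SAP*

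**What the plan says.** Protocol 12.4.4 states that "only the response assessment performed at Cycle 7 Day 1 or the response assessment performed 6 months after starting the study treatment is considered". It labels an incomplete assessment as unknown, and it accepts an adequate CR or CRi "even if one or several inadequate response assessments" came before it. It does not say how to classify a participant with no adequate assessment at either time point.

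SAP 2.5.4 covers that participant with three bullets. If the Cycle 7 Day 1 or 6-month assessment is missing or unknown, the subsequent assessment decides:

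- CR or CRi makes the participant a responder: "If no relapse (maintenance of CR or CRi) is documented at the subsequent response assessment (any time after Cycle 7 Day 1", or after 6 months for those who did not complete 6 cycles.
- Relapse makes the participant a non-responder.
- A subsequent assessment that is also missing or unknown makes the participant a non-responder.

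The efficacy question in SAP 1.2.1 asks about prevention of relapse "until use of donor lymphocyte transfusions (DLIs) or other new antineoplastic therapies". Its intercurrent-event rule says that "a participant who starts a DLI or a new antineoplastic therapy before completing 6 cycles of treatment will be considered as a non-responder".

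On arm membership, Protocol 12.1 analyses participants by treatment received, while SAP 2.2 uses assigned treatment and SAP 2.5.2 uses the enrolled cohort. SAP Section 4, on changes to protocol-specified analyses, is marked not applicable.

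**The concern.** The two documents give different rules for the same primary endpoint. The protocol limits which assessment counts, whereas the SAP admits a later one with no upper time limit.

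The SAP's rule also lacks a condition that its own secondary endpoints carry. In SAP 2.6.1, RFS and GRFS are censored at the last adequate assessment before DLI or new therapy, and MRD conversion uses only samples taken before either. The intercurrent-event rule in SAP 1.2.1 stops at completion of 6 cycles. Therapy started after cycle 6 but before the later assessment is therefore covered by neither rule. At stake is whether a relapse treated with DLI or new therapy can be reported as absence of relapse, contrary to the efficacy question.

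**Working it through.** **The plan's own figures.** Protocol 12.8.1 requires at least 8/25 (monotherapy, null 15%) and 11/20 (combination, null 30%). Exact binomial tails reproduce the printed operating characteristics:

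- P(X ≥ 8 | 25, 0.15) = 0.0255 (printed 2.5%); power is 0.694 at 35% and 0.846 at 40%.
- P(X ≥ 11 | 20, 0.30) = 0.0171 (printed 1.7%); power is 0.755 at 60%.

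**Which cases remain open.**

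1. DLI or new therapy before completing 6 cycles is already non-response (SAP 1.2.1). The open case needs 6 completed cycles.
2. The Cycle 7 Day 1 assessment must be missing or unknown. That visit is day 6 × 28 + 1 = 169. The next scheduled assessment, Cycle 10 Day 1, is day 9 × 28 + 1 = 253, which is 84 days later.
3. A relapse must occur and stay undocumented, although Protocol 8.3.1 says "Clinical suspicion of relapse at any time will require an evaluation promptly, rather than waiting for the next scheduled assessment".
4. DLI or new therapy must then start. Protocol 6.2.2 says "Post treatment efficacy follow-up period will end, once a participant develops a hematologic relapse, or start of new therapy for AML", and Section 9.1.1.2 agrees. Tables 8-1 and 8-2 run the scheduled marrow, extramedullary and response assessments, EOT included, only until relapse or new therapy.
5. CR or CRi must then be recorded. Given step 4, this means a clinically indicated or unscheduled assessment, which the same tables and Section 8.3.1 allow, or a DLI that is not treated as new therapy.

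A participant meeting all five conditions is a responder under SAP 2.5.4.

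**Weight of one participant.** 1/25 = 4 percentage points; 1/20 = 5 points. Exact (Clopper-Pearson) 95% intervals at the planned sizes:

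| Count | Interval |
|---|---|
| 7/25 | 12.1–49.4% |
| 8/25 | 14.9–53.5% |
| 10/20 | 27.2–72.8% |
| 11/20 | 31.5–76.9% |

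**Expected frequency.** The documents give none, so all three inputs are assumptions:

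- a, Cycle 7 Day 1 missing or unknown: 5–20%.
- b, of those, undocumented relapse followed by DLI or new therapy before any adequate assessment: 2–10%.
- c, of those, CR or CRi then recorded: 10–50%.

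The rate per participant is m = a × b × c. Type I error is taken at a null rate of p0 + m.

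| a × b × c | m | 25m | 20m | Type I, 8/25 | Type I, 11/20 |
|---|---|---|---|---|---|
| none | 0 | 0 | 0 | 2.55% | 1.71% |
| 0.05 × 0.02 × 0.10 | 0.0001 | 0.0025 | 0.002 | 2.56% | 1.72% |
| 0.10 × 0.05 × 0.30 | 0.0015 | 0.0375 | 0.03 | 2.69% | 1.78% |
| 0.20 × 0.10 × 0.50 | 0.010 | 0.25 | 0.20 | 3.61% | 2.20% |

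**The case against.** The strongest reply is that SAP 2.5.4 fills a gap rather than overturning a rule. The protocol does not classify a participant with neither assessment, and its closing sentence tolerates earlier inadequate ones. Part of this stands: some rule was needed, and this one was written before database lock. But the closing sentence does not say that a later visit may replace the landmark, and the word *only* limits which assessment counts. The SAP rule is still a change.

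Second, the open case stacks several departures from planned conduct, and scheduled efficacy assessment already stops at new therapy. A reader might take the EOT visit, which "should be scheduled for an end of treatment (EOT) visit within 14 days from the decision to permanently discontinue study treatment" (Protocol Section 8), as an easy route to a remission recorded after rescue. It is not: the schedules limit that assessment too. This stands, and it is why the point is minor.

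Third, Section 2.5.4 is headed as unrelated to intercurrent events, with DLI and new therapy handled in 1.2.1. That would answer the point if 1.2.1 covered starts after cycle 6, but it does not.

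Fourth, a DLI given without relapse does not make the landmark status wrong, so a date condition has its own cost. This also stands.

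**Conclusion.** The concern holds as a narrow gap in the primary endpoint rule, plus an incomplete record of changes. Under the stated assumptions the expected effect is at most a quarter of a participant at n = 25. Type I error at the planned cuts would move from 2.5% to at most 3.6%, and from 1.7% to at most 2.2%. The planned cuts carry little weight after the recruitment halt, and SAP 2.5.2 drops the p-value. The endpoint is still selected for the final report in SAP Table 1-1, and with fewer participants each one weighs more in the proportion.

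Three stronger readings might be inferred and are not supported.

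- *The fill generally inflates response.* Without intervening therapy it does not: a relapse found at the later visit counts as failure, and so does a second missing or unknown result.
- *Type I error is seriously inflated.* If 2–10% of true non-responders were reclassified, success at the monotherapy null would have probability 4.5–21.7%. Even the low end means 0.85 × 2% = 1.7% per participant, above the 1.0% maximum assumed here, and nothing in the documents suggests such rates.
- *The trial's conclusion hangs on this rule.* One participant does separate failure from success at 7/25 or 10/20, but enrolment stopped early and the documents give no final counts.

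The arm-membership difference is rarely consequential. Protocol 12.1 illustrates it with a participant randomized to the combination who receives no azacitidine; Protocol 6.1.1 calls for at least 5 azacitidine doses before the first sabatolimab infusion.

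**What to change.** Keep the three bullets of SAP 2.5.4, including non-response when the subsequent assessment is also missing or unknown, and add:

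*The subsequent response assessment is used only if dated before the start of any DLI or new antineoplastic therapy; otherwise the participant is a non-responder.*

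The bullets should not be rewritten to use the first subsequent adequate assessment. That would loosen the rule: a participant with Cycle 7 Day 1 missing, Cycle 10 Day 1 unknown and CR at Cycle 13 Day 1 would change from non-responder to responder.

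For the record, list two entries in SAP Section 4 in place of the present statement: the missing-assessment rule, and arm membership (received versus assigned). The arm-membership passages in Protocol 12.1 and SAP 2.2 and 2.5.2 should be reconciled.

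The cost is one sentence and two entries, plus that reconciliation. No new data are needed, because DLIs and all response assessments are already to be listed (SAP 2.4.2 and 2.6) and antineoplastic therapy after discontinuation is collected. The downside is that a participant given DLI without relapse after 6 cycles, with no earlier adequate assessment, would count as a non-responder although relapse-free at the landmark. The documents do not show whether this is rarer than the case being closed.

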2.5.5 Sensitivity analyses

Not applicable.

2.5.6 Supportive analyses

Not applicable.

2.6 Analysis of secondary objective(s)

Secondary efficacy endpoints will be analyzed and summarized for the FAS and by dose cohort (Adults with sabatolimab 400 mg, Adults with sabatolimab 800 mg, Adults with azacitidine and sabatolimab combination, Adolescents with sabatolimab monotherapy).

A listing of all responses assessments by participant will be provided.

